**VERSION: 7.0 (23 FEB 2024)**

**FUNDING SOURCE: Morningside Center**

## REVISION HISTORY

Revision #	Version Date	Summary of Changes
1.0	26Mar2020	First version submitted to Emory IRB
2.0	27Aug2020	Second version with minor clarifications and specification of sample collection visit windows.
3.0	24Nov2020	Third version with minor dosing clarification.
4.0	19Feb2021	Fourth version with minor exclusion eGFR level changes
5.0	27Jan2022	Fifth version with increased overall enrollment goal of up to 100 patients to account for screen fails and/or withdrawals
6.0	31 Mar 2022	Sixth version with minor clarification regarding tissue collection including malignant and benign tissue.
7.0	23 FEB 2024	Ceasing enrolment for the Cardiothoracic group

## 1. Study Summary

Study Title	A Pilot Study of Biomarker Evaluation and Safety of Pre-Incisional Ketorolac for Patients Undergoing Surgical Resection for Non-Small Cell Lung Cancer and Renal Cell Carcinoma
Study Design	
PATIENT REGISTRATION/RANDOMIZATION
 
Patients will be screened and recruited during the pre-operative period by the responsible medical and surgical team. Blood will be drawn pre-operatively and then at the end of the surgical procedure. Patients who are eligible to be included will be fully informed, consented for additional blood draws and will have the opportunity to ask any questions they may have.
 
Patients will be randomized to either pre-operative Ketorolac group or a concurrent control group who will not receive pre-incisional ketorolac. The concurrent control group is to obtain untreated biologic samples for biologic correlative studies and secondary endpoints. These patients will not be compared to the investigational cohort in regards to the primary endpoint of safety. Patients will be randomized on the day of surgery to either the experimental or control arms. A total of 56 patients will be enrolled into the experimental arm (28 per disease site). About 10 patients will be allocated randomly into the concurrent control group for each disease site separately, for a total of 76 patients enrolled. The enrolment for NSCLC will cease at total of 28 patients consented with total study enrolment goal of 79 Up to 80 patients may be consented on study to account for screen fails and/or withdrawals.

Primary Objective	To test the safety of a single pre-incisional dose of 30 mg ketorolac in patients undergoing surgery for stage I/II NSCLC and stage III RCC, as these are the stages of cancer most likely to develop a recurrence while still noting a benefit from the ketorolac.
Secondary Objective(s)	To evaluate blood and tissue samples pre- and post-operatively to assess the impact of ketorolac on key

	inflammatory biomarkers using a standard cytokine panel.
Research Intervention(s)/Interactions	STUDY PROCEDURES  Surgical Resection All patients will receive standard-of-care surgery. Open, video-assisted thoracic surgery, laparoscopy, or robotic surgery are allowed. Standard anesthesia will be administered.  Ketorolac 30 mg ketorolac will be administered intravenously during the induction of anesthesia (pre-incision). Ketorolac administration will not be permitted during the operation. Patients randomized to the control group will not receive Ketorolac.
Study Population	See Inclusion Criteria and Exclusion Criteria.
Sample Size	See Statistical Consideration
Study Duration for individual participants	2 years
Study Specific Abbreviations/ Definitions	N/A
Funding Source (if any)	Morningside Center

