## 9. Study Timelines

The study will be closed to enrollment for all patients. Only RCC participants are expected to participate in the study for 2 years. All study related assessments and activities to cease for NSCLC participants. The estimated date for investigators to complete this study is March 1, 2025.

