## 16.2 Statistical Consideration

### 16.2.1 Sample size determination

It is a pilot study that aims to monitor the hemorrhage side effects who received Ketorolac pre-operatively with the primary safety endpoint being pre-discharge blood transfusion. According to the historical data, among 3280 nephrectomy cases during 2015-2020 in Emory, 20% need a blood transfusion before the discharge, and the mean number of units transfused is 0.286 (standard deviation = 0.12). Among 1212 thoracotomy cases during 2014 -2020 in Emory, 3.4% need a blood transfusion before the discharge, and the mean number of units transfused is 0.098 (standard deviation = 0.075). We anticipate a similar safety profile among the patients who received the pre-operative Ketorolac in this study. A sample size of 50 (25 patients in each disease site) produces a one-sided 90% confidence interval with an upper limit of 0.12 (the distance from the mean number of units transfused to the upper limit = 0.02) for thoracotomy. For nephrectomy, the upper limit of a one-sided 90% confidence interval would be 0.318 (the distance from the mean number of units transfused to the upper limit = 0.032). To account for a possible 10% drop off, we will plan to enroll 28 patients in each disease type.

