#### 16.2.2 Stopping Rule

The PIs will monitor the blood transfusion ordered and the units transfused before patients' discharge. In any case, blood transfusion with more than 2 units (BT2U) happens, the trial will pause to examine the cause and decide whether to continue or terminate the trial due to the safety concern. The trial will be terminated if the accumulative relevant BT2U number reaches to six for nephrectomy (24%) or two for thoracotomy (8%). The stopping rule is to stop the trial early due to any high chance of toxicity.

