## 21. Resources Available

There are hundreds of resections for Non-Small Cell Lung Cancer and Renal Cell Carcinoma each year. Within 5 years of recruiting, the goal of 76 patients enrolled is feasible. 50% of one full time research coordinator's effort will be devoted to this trial annually. Medical and psychological resources that participants might need as a result of an anticipated consequences of the human research are available at Emory.

A dedicated clinical research team will be available to assist in proper conduct of this research study. There will be extensive documentation of training for study personnel. This will be documented on training forms, delegation of authority forms, the 1572, and other documents. Training is ongoing and will be updated as needed.

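### The cap of 28 consented NSCLC patients does not fit the 28 ketorolac patients (25 evaluable) per site that the sample size and the lung stopping percentage still assume, and enrolment totals and status conflict

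*Combined protocol and SAP*

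**What the plan says.** Section 1 (Study Design) sets the arm size: "A total of 56 patients will be enrolled into the experimental arm (28 per disease site"). On controls it says: "About 10 patients will be allocated randomly into the concurrent control group for each disease site separately, for a total of 76 patients enrolled". On timing it says: "Patients will be randomized on the day of surgery to either the experimental or control arms". The same paragraph then caps the lung cohort: "The enrolment for NSCLC will cease at total of 28 patients consented with total study enrolment goal of 79". It also lets up to 80 be consented, to cover screen failures and withdrawals.

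Section 16.2.1 gives the precision: "A sample size of 50 (25 patients in each disease site) produces a one-sided 90% confidence interval with an upper limit of 0.12". It states the lung distance from mean to limit as 0.02, and raises 25 to 28 per disease type for a 10% loss.

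Section 16.2.2, on transfusions of more than two units, says: "The trial will be terminated if the accumulative relevant BT2U number reaches to six for nephrectomy (24%) or two for thoracotomy (8"%).

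On enrolment, Section 9 states: "The study will be closed to enrollment for all patients". Section 12 ends enrolment for NSCLC only. Section 11 gives up to 80 patients. Section 21 says that "the goal of 76 patients enrolled is feasible".

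**The concern.** The cap counts consented patients, whereas the 28 per site in Section 1 counts ketorolac patients. Consent comes before allocation on the day of surgery, so the capped 28 must supply the ketorolac arm, the controls and any screen failures or withdrawals. Section 16.2.3 limits the safety summaries to ketorolac recipients, so controls cannot fill the gap. Section 6.3 also leaves patients with benign pathology out of the analysed number.

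Safety is the primary objective and lung is one of two cohorts. As written, a reader cannot tell how many lung patients will support the safety conclusion, what share of them the two-event boundary represents, or whether RCC accrual is still open.

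**Working it through.** **Inputs.** Section 16.2.1: lung mean 0.098 units, SD 0.075; nephrectomy mean 0.286, SD 0.12; 25 evaluable per site; one-sided 90%; 10% loss. Section 16.2.2: boundaries of six and two. Section 1: 28 ketorolac and about 10 controls per site, NSCLC cap 28, goal 79. The 28:10 ratio is implied by these counts; no ratio is stated.

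**Reproducing the plan at n = 25.** Distance = t(0.90, n−1) × SD/√n.
- Lung: 0.0198, limit 0.098 + 0.0198 = 0.1178 (stated 0.02 and 0.12).
- Nephrectomy: 0.0316, limit 0.286 + 0.0316 = 0.3176 (stated 0.032 and 0.318).
- Enrolment: 25/0.9 = 27.8, so 28.
- Boundaries: 6/25 = 24% and 2/25 = 8%.

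All stated figures reproduce, so 25 per site is their basis.

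**What the cap allows.** To have 28 lung ketorolac patients there must be no controls and no losses. To have 25 there can be at most 28 − 25 = 3 controls and losses combined. At a 28:10 split, the chance that 25 or more of 28 are allocated ketorolac is about 4% with independent assignment (binomial, p = 28/38). It is below 0.1% from a fixed list of 28 + 10 (hypergeometric). Both are before any losses.

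**Lung ketorolac n under the cap.**
- Implied split: 28 × 28/38 = 20.6, about 21; after 10% loss 18.6, about 19.
- All 10 controls filled: 28 − 10 = 18; after 10% loss 16.2, about 16.

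| Lung n | Distance | Upper limit | Two events |
|---|---|---|---|
| 25 (plan) | 0.0198 | 0.1178 | 8.0% |
| 21 | 0.0217 | 0.1197 | 9.5% |
| 19 | 0.0229 | 0.1209 | 10.5% |
| 18 | 0.0236 | 0.1216 | 11.1% |
| 16 | 0.0251 | 0.1231 | 12.5% |

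The distance grows by about 10% (0.0217/0.0198) to 27% (0.0251/0.0198). Every limit in the table still rounds to 0.12.

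**RCC.** 79 − 28 = 51 places against 28 + 10 = 38 planned, so 13 are extra. No arm or purpose is attached to them. Twenty-five evaluable ketorolac patients, and so 6/25 = 24%, remain attainable.

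**Check on the SD.** If 3.4% are transfused and the overall mean is 0.098, those transfused average 0.098/0.034 = 2.88 units. The smallest possible SD is then √(0.034 × 2.88² − 0.098²) ≈ 0.52, not 0.075. With that minimum, the distance at n = 25 is about 0.138. This is a separate problem and larger than the effect of the cap.

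**The case against.** The strongest reply is that little of operational weight changes. The stopping rule works on counts, which remain usable; the percentages stand only in brackets. Lung enrolment is ending, so the lung boundary has little prospective role left. The safety summaries in Section 16.2.3 are descriptive and will use whoever was treated. The printed lung limit of 0.12 survives rounding. All of this stands, and it limits the severity.

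It can also be said that Section 1 never states that the 28 spans both arms. That is true. It is an inference, but the natural one, because the cap is on consent and allocation comes later. The match between the cap of 28 and the 28 per disease type in Section 16.2.1 may suggest that nothing has changed, but Section 1 ties the latter figure to the ketorolac arm.

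Four stronger readings are tempting and not supported:
- **25 evaluable lung patients are impossible.** They are unlikely under the implied split, not excluded.
- **The nephrectomy boundary has shifted.** A reader might apply 28:10 to the 51 RCC places, get about 38 on ketorolac, and call six events 16%. Section 1 still fixes ketorolac at 28 per site and states no ratio. The extra places might be a consent allowance, which Section 1 attaches to the figure of 80. The 38 is also before loss, whereas the plan's 25 is after it.
- **The plan loses a stated precision on the transfusion rate.** Section 16.2.1 gives one-sided 90% precision for mean units only. For the rate, Section 16.2.3 specifies 95% intervals, so one-sided 90% rate limits are not a property of this plan.
- **Precision and stopping percentages are the only statistical properties stated.** Section 16.2.3 also specifies intervals, and Section 16.3 a two-sided test at 0.05.

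**Conclusion.** The inconsistency is real and should be fixed. It does not invalidate the trial. The current text promises 28 ketorolac patients (25 evaluable) in the lung cohort and caps that cohort at 28 consented. The lung n is therefore more likely about 16 to 21, assuming a 28:10 split or all 10 controls filled, and 0 to 10% loss. Screen failures and benign pathology, for which no numbers are given, would lower it further.

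The precision loss is small on the plan's own SD. The lung 8% is out of date. The nephrectomy 24% holds if RCC ketorolac stays at 28 enrolled. The conflict between Sections 9 and 12 on enrolment, the coexisting totals of 76, 79 and 80, and the 13 unexplained RCC places need no assumption: they are in the current text.

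**What to change.** - Reconcile Sections 1, 9, 11, 12, 16.2.1, 16.2.2 and 21 to one table of consented, randomised and evaluable counts by site and arm.
- State whether the NSCLC cap covers both arms, whether RCC enrolment is open, and what the 13 further RCC places are for.
- Check the SDs in Section 16.2.1 against the stated transfusion rates and means before reusing them; otherwise the restated precision repeats a doubtful input at a new n.
- Then restate the lung n and lung precision in Section 16.2.1, and the lung percentage in Section 16.2.2, at the ketorolac number actually available. This concerns the denominator of the percentage; whether the count boundary itself should change is outside this point.

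The cost is protocol wording and a short recalculation. On the plan's own SD the stated lung precision becomes slightly less favourable. No extra patients are needed.

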## 2. Objectives

### 2.1 Primary Objective

To test the safety of a single pre-incisional dose of 30 mg ketorolac in patients undergoing surgery for stage I/II NSCLC and stage III RCC, as these are the stages of cancer most likely to develop a recurrence while still noting a benefit from the ketorolac.

### 2.2 Secondary Objective

To evaluate blood and tissue samples pre- and post-operatively to assess the impact of ketorolac on key inflammatory biomarkers using a standard cytokine panel.

## 3. Introduction and Background

[figure not shown]
Surgical resection is a cornerstone of standard-of-care treatment for early-stage non-small cell lung carcinoma (NSCLC) and renal cell carcinoma (RCC). Yet despite optimal treatment, many of these patients will develop cancer recurrence within the first few years. For example, the 5-year

survival rate for patients with stage I/II NSCLC is only around 55%. As a result, more effective treatments that decrease cancer recurrence and increase survival are still needed.

Surgery induces inflammation, immunosuppression and angiogenesis. Although these processes are important for wound healing in response to tissue injury caused by surgery, they also support the survival, growth and dissemination of any remaining cancer cells and can lead to systemic recurrence soon after surgery. Surgical trauma increases the production of prostaglandins and thromboxanes, which have tumor-promoting and immunosuppressive activities, and reduces the activity of natural killer cells, which impairs the ability of the immune system to keep cancer cells in check. However, if given just before tissue injury, non-steroidal anti-inflammatory drugs (NSAIDs) may be able to block the production of prostaglandins/thromboxanes and boost the activity of natural killer cells, and thereby decrease the risk of cancer recurrence. Indeed, NSAIDs have anticancer effects in animal models and humans. For example, in one study, the 20-year risk of cancer-related death was significantly lower after administration of daily aspirin (HR 0.80,  $p<0.0001$ ).

NSAIDs such as ketorolac are already routinely given to cancer patients post-operatively for pain management and are sometimes given intra-operatively (immediately before or during surgery) to prevent post-operative pain. A retrospective clinical analysis found that intra-operative intravenous ketorolac or diclofenac (another NSAID), when added to standard of care for patients with stage I/II NSCLC, was associated with decreased risks of distant recurrence (HR = 0.50; 95% CI 0.24-1.00;  $P = 0.05$ ) and mortality (HR = 0.64; 95% CI 0.42-0.96;  $P = 0.03$ ) (Figure 1). Similar results were seen in renal cell carcinoma (RCC).

**Figure 1.** Kaplan-Meier curves of overall survival for 255 patients receiving or not an NSAID (ketorolac or diclofenac) intra-operatively during NSCLC surgery. Univariate analysis by log-rank test. Figure from .

The effect of intra-operative NSAIDs may be even more prominent in patients with pre-operative inflammation, which is associated with a greater risk of early recurrence and mortality. Moreover, recent data indicates that **pre-operative**, but not post-operative, ketorolac administration can eliminate micrometastatic disease in animal lung and breast cancer resection models and create long-lasting T cell immunity. Thus in addition to safety and feasibility, we will assess whether there is evidence of a tumor directed T-cell response in patients who receive pre-operative ketorolac.

We do note a recently published randomized phase III study in breast cancer failed to identify a reduction in recurrence rates in high-risk breast cancer patients, and did not support retrospective data which did show a benefit. Though many possibilities exist for the negative results of this most recent study, one possibility is that chemotherapy was utilized in the majority of the patients, and arms were somewhat imbalanced. This may have negated the effect of the ketorolac, as noted in our preclinical animal studies.

**Given these overall findings, there is significant promise in the use of preoperative ketorolac to decrease the inflammatory response after surgical resection of tumors, thereby potentially reducing the risk of distant metastatic tumor spread and improving survival.** These results could potentially be applied to any number of tumor sites. However, ketorolac and other NSAIDS inhibit platelet function by blocking cyclooxygenase enzymes and the formation of thromboxane A2, resulting in potentially higher risk for postoperative bleeding or result in higher rates of postoperative renal failure. *While the risk of such complications after a single dose of ketorolac is likely low, the safety of a preoperative dose of ketorolac prior to major surgical resection needs to be assessed* prior to proceeding with a larger phase II study designed to evaluate traditional efficacy endpoints such as recurrence and overall survival. Additionally, the proposed mechanism that ketorolac effect is T-cell dependent and contributes directly to anti-tumor activity via reduction of postoperative inflammation can be further studied. Blood and tissue samples from patients enrolled in this study will be analyzed to determine if the effect of ketorolac is more prominent in patients with high pre-operative inflammation.

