## 7. Data and Specimen Banking

### 7.1 Biological Correlative Studies

The specific effects of ketorolac on the host immune system are not known. It is hypothesized that pre-operative ketorolac will enhance anti-tumor immunity and result in activation of tumor-specific T cell responses, as has been noted in our preclinical studies. To verify this, we will collect tissue samples, including surrounding benign and malignant tissue as part of the standard surgical procedure, and peripheral blood at pre-specified time-points. The following samples will be collected from all patients on this trial:

1. Tumor tissue at the time of surgery - Tissue will be collected from patients at the time of surgery by clinical research coordinators from the Clinical Research Unit and taken to [name] lab if adequate tissue is available after all necessary clinical samples are obtained as determined by the pathologist. Tissue analysis will be performed on malignant and benign tissue.
2. Serum and PBMCs before and at time points after surgery - Blood will be collected in CPT from patients at the time of surgery and postoperatively, as delineated in the timeline, by clinical research coordinators.

The following studies are planned in the bio-specimens collected: 1. Flow cytometry (at least to assess proliferating and activated T-cells in blood); 2. TCR sequencing to assess diversity of the T cell repertoire intra tumorally and in blood; and 3. Single cell RNA Seq in blood. Samples will be suitably prepared to allow for this at a future date. Collectively these assays will provide evidence for whether pre-op ketorolac can unleash post-operative anti-tumor T cell response in humans, thus extending the mouse data above. In addition, we will measure NLR, CRP, and IL-6 – all of which have been correlated to prognosis in a number of tumor types at baseline and some of which have been correlated to recurrence outcomes. Additional exploratory studies may also be conducted based on the results of these studies. Peripheral blood mononuclear cells (PBMCs) and plasma will be isolated from CPTs and cryopreserved. The correlative work will be conducted in the lab of [name], [name] and [name].

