Tissue analysis: In this proposal, we will measure how organization of immune cells in the tumor change after treatment. The tumor architecture and immune organization will be examined via IF and this imaging data will be quantitatively analyzed. We will determine the relative infiltration of stem-like T-cells, effector-like T-cells, and DCs, lymphatic and blood vessels. We will measure the distance between cells, and quantify their aggregation. We will specifically quantitate regions of sufficient antigen presenting density (5 APCs/100um^2) that are generated following implantation of the niche, and how these regions are located relative to the implant. A specific focus of this work will be how lymphatic and vasculature is altered before and after treatment and how this correlates with response to therapy.

Serum analysis: We will measure NLR, CRP, and IL-6 – all of which have been correlated to prognosis in a number of tumor types at baseline and some of which have been correlated to recurrence outcomes.

PBMC analysis: In ongoing work we have collected blood and tissue from patients receiving checkpoint blockade therapies at Emory and studied the immune response of these patients. We have found that in the blood of patients that have a clinical response to checkpoint therapy, there is a proliferative burst of newly generated effector CD8 T-cells in the blood. In comparison, patients that do not have clinical response to the treatment fail to generate this population of cells. This marker has significant predictive power to identify which patients will respond after the first treatment cycle with PD-1

blockade. In this proposal we will determine if measuring this marker after surgery and treatment with Ketorolac is associated with improved response to treatment.

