#### 16.2.4 Analysis of the secondary endpoints

For all biomarkers, descriptive statistics (means, medians, standard deviations, interquartile range) and graphical displays will be used to characterize central tendency and variability over time. Values will be log transformed as appropriate to reflect biologic plausibility.

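### Nothing in the plan's analysis can show whether ketorolac's effect is greater with high pre-operative inflammation, and the control group is too small to do more than explore it

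*Combined protocol and SAP*

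**What the plan says.** - **Aim.** Section 3 ends by saying that samples "will be analyzed to determine if the effect of ketorolac is more prominent in patients with high pre-operative inflammation". This aim does not reappear in the objectives (Section 2), the endpoints (Section 4) or the statistical section (16.2).
- **Secondary objective.** Section 2.2 is broader: "to assess the impact of ketorolac on key inflammatory biomarkers using a standard cytokine panel". Section 4.2 describes the correlative studies as exploratory.
- **Markers.** Section 7.1 lists three candidates ("we will measure NLR, CRP, and IL-6") and describes them as "all of which have been correlated to prognosis in a number of tumor types at baseline". None is chosen to define high inflammation, and no cut-off is given.
- **Analysis.** For all biomarkers, Section 16.2.4 states that "descriptive statistics (means, medians, standard deviations, interquartile range) and graphical displays will be used to characterize central tendency and variability over time". It adds: "Values will be log transformed as appropriate to reflect biologic plausibility". It mentions no contrast between arms, baseline stratum, baseline adjustment or interaction.
- **Controls.** Section 1 randomises about 10 controls per disease site against 28 treated, and gives the reason: "The concurrent control group is to obtain untreated biologic samples for biologic correlative studies and secondary endpoints". Only the primary safety comparison excludes them. Section 1 also stops NSCLC enrolment at 28 consented.
- **Baseline samples.** The collection table in Section 7.2 lists two pre-surgery samples, one at the anaesthesia visit and one on the day of surgery.

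**The concern.** Whether a drug works better in inflamed patients is a question of effect modification. It needs the ketorolac-minus-control difference as a function of baseline inflammation. A summary over time that does not compare the arms cannot supply it, because surgery itself moves these markers.

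Section 16.2.4 also leaves an analyst without direction. One natural way to pursue the Section 3 aim would be to split treated patients by baseline level and describe the change in each half. For the same marker, or one correlated with it, that comparison is open to regression to the mean and can suggest a subgroup effect where there is none. Even the valid comparison rests on about five controls in each half of a site, which sits badly with a promise to determine the answer.

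**Working it through.** **1. The plan's own figures.** The documents give no sample-size or precision figure for this question. The only ones, in Section 16.2.1, concern units transfused. They reproduce with t(0.90, 24 df) = 1.318: 0.098 + 1.318 × 0.075/√25 = 0.118 (stated 0.12) and 0.286 + 1.318 × 0.12/√25 = 0.318 (stated 0.318). They have no bearing on the biomarker aim.

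**2. A split within the ketorolac arm, with no drug effect.** Take baseline and follow-up as bivariate normal with correlation ρ and k = SD after / SD before. The documents give neither, so both are assumptions. After a median split the halves have mean baselines of ±√(2/π) = ±0.798 SD. The expected high-minus-low gap in change, in baseline SDs, is

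gap = (ρk − 1) × 2 × 0.798 = 1.596 × (ρk − 1).

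| ρ | k | gap (SD) |
|---|---|---|
| 0.7 | 1 | −0.48 |
| 0.5 | 1 | −0.80 |
| 0.3 | 1 | −1.12 |
| 0.5 | 2 | 0.00 |
| 0.7 | 1.5 | +0.08 |
| 0.7 | 2 | +0.64 |

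A negative gap looks like a larger benefit in inflamed patients. In simulation (4,000 runs per setting, 28 treated, k = 1), the high half fell more or rose less in 95% of trials at ρ = 0.7 and in 99% at ρ = 0.5. It did so with p < 0.05 in 37% and 58%.

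**3. The same split compared with controls.** Controls regress to the mean in the same way. In the k = 1 simulations with ρ from 0.5 to 0.9, the treated gap minus the control gap was 0.00 to 0.02 SD in size. The arm-by-baseline interaction test had a type I error of 0.046 to 0.052. At ρ = 0.6, k = 2 the corresponding values were 0.00 and 0.048.

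**4. Precision of the valid contrast.** With each arm split in half, the SE of the high-versus-low difference in effect, in residual SDs, is √(4/n_treated + 4/n_control). The difference detectable at 80% power (two-sided 0.05) is 2.802 × SE.

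- One site, 28:10: SE = √(4/28 + 4/10) = 0.737; detectable 2.06 SD; power for a 1 SD difference 27%.
- Both sites as first sized, 56:20: SE = √(4/56 + 4/20) = 0.521; detectable 1.46 SD; power 48%.
- Both sites with NSCLC stopped at 28 consented, split about 21:7 (assumed, near the 28:10 ratio), and RCC at 28:10, giving 49:17: SE = √(4/49 + 4/17) = 0.563; detectable 1.58 SD.

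The last line keeps RCC at its stated per-site size. Section 1 also gives a total goal of 79, which would leave 79 − 28 = 51 for RCC. At the same ratio that is about 38:13, or 59:20 pooled: SE = √(4/59 + 4/20) = 0.518; detectable 1.45 SD. The conclusion is the same.

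**5. Gain from a continuous baseline.** With a normal baseline, the interaction slope at 28:10 has SE √(1/28 + 1/10) = 0.368 per baseline SD. Scaled to the distance between the halves, the detectable difference is 2.802 × 0.368 × 1.596 = 1.65 SD, against 2.06 for the split. This is better, but still large.

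**The case against.** The strongest reply is that the plan prescribes no faulty analysis. Section 16.2.4 is silent on splitting by baseline, and Section 1 provides randomised controls for exactly these secondary endpoints. The aim sits in the background section of a pilot whose correlative studies are already called exploratory.

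Much of this stands. A reader might infer that the planned summaries will show a greater effect in inflamed patients from regression to the mean alone. The documents do not support that, for three reasons:

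- No within-arm split is specified.
- The artefact in that direction needs ρk below 1. Section 3 itself says that surgery induces inflammation, so k may well exceed 1.
- The outcome must be the classifying marker or one correlated with it. This does not follow automatically for flow cytometry, TCR sequencing, single-cell RNA or tissue readouts.

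A reader might also infer that a false result would decide who enters the phase II trial. Section 3 makes the safety assessment the precondition for that trial and says nothing about selecting patients on inflammation.

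The reply does not remove the gap. Having controls is not the same as planning to compare with them, and Section 16.2.4 never does. The exploratory label in Section 4.2 also conflicts with the promise in Section 3 to determine the answer.

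**Conclusion.** The point holds as a gap between a stated aim and its analysis. Section 3 promises an answer on effect modification; Section 16.2.4 contains no ketorolac-versus-control contrast from which to obtain one, and neither the marker nor 'high' is defined.

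Regression to the mean is a conditional risk, not a prediction. It amounts to 0.48 to 1.12 baseline SD for ρ from 0.7 to 0.3 if the SDs are equal, and it can vanish or reverse otherwise. It applies only if the ketorolac arm is split on its own. In either direction the pattern would be spurious, and the controls remove it.

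Precision does not depend on that risk. The detectable difference is about 2.06 residual SD in a site at 28:10. Pooled, it is about 1.58 SD if NSCLC contributes 21:7 and RCC 28:10, which is worse than the 1.46 SD at 56:20. The study can explore this question but cannot settle it.

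**What to change.** Add to Section 16.2.4:

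- Effect modification is estimated as the arm-by-continuous-baseline interaction in a model of the log post-operative value, at a stated time point, with arm, log pre-dose value and disease site.
- The sponsor names one baseline inflammation marker in advance from NLR, CRP and IL-6. The documents do not rank them, so the choice is the sponsor's. The plan states which of the two pre-surgery samples in Section 7.2 supplies the baseline.
- The interaction is reported with its 95% CI as exploratory.
- No conclusion on effect modification is drawn from high-versus-low comparisons within the ketorolac arm alone.

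In Section 3, change 'determine if' to 'explore whether'.

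The cost is one extra model and a weaker claim in Section 3. No new data are needed; this matters because Section 9 closes enrolment, so the analysis is the part that can still be improved.
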